AML=acute myelogenous leukemia; BM=bone marrow; C1D1=cycle 1 day 1; ECOG=Eastern Cooperative Oncology Group; HMA= hypomethylating agent; PB=peripheral blood; WBC=white blood cell. Note 1: Only 2 subjects had more than 1 month prior HMA therapy.

Source: CSR SGI-110-01-B Table 14.2.1 and, for prior HCT, Appendices 16.2.9.1 and 16.2.11

Overall, 24 of 103 subjects with AML who were either refractory to prior treatment or relapsed after achieving a CR from induction therapy responded to treatment with guadecitabine (Table 2). The overall CRc rate was 23.3% (95% CI: 15.5-32.7). Of these 24 responders,

14 achieved a best response of CR, 6 achieved a best response of CRi, and 4 achieved a best response of CRp.

The CRc and CR rates of the 10-day regimen were approximately double that of the 5-day regimen (10-day CRc and CR rates, 30% and 19%, respectively; 5-day CRc and CR rates, 16% and 8%, respectively).

In the 5-day regimen, the CR and CRc rates were generally not different between 60 and 90 mg/m² (8.3% and 7.7% for CR, and 12.5% vs 19.2% for CRc for the 60 and 90 mg/m² dose groups, respectively).

Of the 24 responders, 5 had prior HCT and 8 had poor cytogenetic risk factors at baseline, and all responders who had evaluable LINE-1 data achieved at least -20% LINE-1 demethylation.

	Res	[)]			
-		5-Day	10-Day		
	60 mg/m^2	90 mg/m ²	Total	60 mg/m ²	Total
Response Category ^a	(N=24)	(N=26)	(N=50)	(N=53)	(N=103)
Complete response (CR)	2 (8.3)	2 (7.7)	4 (8.0)	10 (18.9)	14 (13.6)
CR with incomplete blood count recovery (CRi)	1 (4.2)	3 (11.5)	4 (8.0)	2 (3.8)	6 (5.8)
CR with incomplete platelet recovery (CRp)	0	0	0	4 (7.5)	4 (3.9)
Partial response (PR)	0	0	0	0	0
Nonresponder (NR)	21 (87.5)	18 (69.2)	39 (78.0)	36 (67.9)	75 (72.8)
Not evaluable (NE) ^b	0	3 (11.5)	3 (6.0)	1 (1.9)	4 (3.9)
CRc rate	3 (12.5)	5 (19.2)	8 (16.0)	16 (30.2)	24 (23.3)
(CR+CRi+CRp)	[2.7 - 32.4]	[6.6 - 39.4]	[7.2 – 29.1]	[18.3 – 44.3]	[15.5 - 32.7]

Table 2:Best Response in Subjects with r/r AML (Efficacy Data Set)

AML=acute myelogenous leukemia; CRc=composite complete response.

^a Modified IWG 2003 AML Response Criteria (Cheson et al 2003).

^b NE subjects are included in the denominator for response rate calculation.

Source: CSR SGI-110-01-B Table 14.3.1.1

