7.3.2.5 Criteria for Response Assessment

The 2003 AML IWG Response Criteria (summarized in Table 1) are used to identify AML subjects with CR, CRp, CRi, or partial response (PR). CRh will also be assessed as a subset of CRi or CRp who have partial hematologic recovery and is defined as <5% of blasts in the bone marrow, no evidence of disease, and partial recovery of peripheral blood counts (platelets $>50,000/\mu$ L and ANC $>500/\mu$ L). Evaluation of response will be conducted by Astex medical monitors assisted by programmed data listings.

Response ^a	Peripheral Blood (PB)	Bone Marrow (BM)
CR	ANC $\geq 1000/\mu$ L, Platelets $\geq 100,000/\mu$ L, independence from RBC and platelet transfusions over the past week, no leukemic blasts ^b	<5% leukemic blasts
CRp	ANC $\geq 1000/\mu$ L, Platelets $< 100,000/\mu$ L, independence from RBC transfusions over the past week, no leukemic blasts ^b	<5% leukemic blasts
CRi	ANC <1000/µL, no leukemic blasts ^b	<5% leukemic blasts
PR	ANC $\geq 1000/\mu$ L, Platelets $\geq 100,000/\mu$ L, no leukemic blasts ^b	Decrease of ≥50% in leukemic blasts to level of 5% to 25%

Table 1:2003 IWG AML Response Criteria

^a Responses are based on both PB and BM conditions.

^b For the purpose of response assessment and according to published IWG criteria, blasts may be seen in PB as rare PB blasts may be identified during regeneration, but the subject is in CR if BM blasts are <5% with no Auer rods (Cheson et al 2003).

ANC=absolute neutrophil count; CR=complete response; CRp=complete response with incomplete platelet recovery; CRi=CR with incomplete blood count recovery; PR=partial response. Source: Cheson et al 2003

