7.3.2.9 Duration of Combined CR and CRh

A combined duration of CR and CRh (in number of days) will be calculated from the first time a CR or CRh is observed to the date of the earliest of the following 3 events: (1) relapse (defined as the earliest time point whereby BM assessment or PB assessment by the investigator indicate relapse/disease progression due to confirmed reappearance of leukemic blasts in PB or $\geq 5\%$ leukemic blasts in BM, or clinical progression determined by the investigator), (2) start of alternative therapy (except HCT) or (3) death. In the absence of any event, the combined duration of CR and CRh will be censored at the last available time point (BM assessment, PB assessment, or safety/long-term follow-up visit) at which an event was not observed. Duration of combined CR and CRh will be analyzed using the Kaplan-Meier method for subjects who achieved a CR or CRh during the study and compared between the two treatment groups using a non-stratified log-

rank test. The median and quartiles of duration of complete response, as well as their respective 95% CIs will be provided. Duration of CR will be calculated and analyzed similarly.

To take the proportion of responders into consideration when analyzing duration of combined CR and CRh, a separate analysis including all subjects will be conducted with a 0-day event duration assigned to subjects who did not achieve a CR or CRh. The median and quartiles of duration of complete response, as well as their respective 95% CIs will be provided.

In addition, both time to first response and time to best response will be calculated and analyzed for subjects who achieve a response of CR, CRp, CRi, or PR. Time to first response is defined as the time, in days, from the date of first treatment (C1D1) to the first date when any response is achieved. Time to best response is similarly defined as the time, in days, from the date of first treatment (C1D1) to the first date when a subject's best response, in the order of CR, CRp, CRi, or PR, is achieved. The times to first response and best response will be summarized by treatment group using mean, standard deviation, median, minimum, and maximum. Time to CR will be summarized similarly.

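### The all-subjects analysis of CR+CRh duration names only the median and quartiles; the median and lower quartile will be 0 in both arms, and no between-arm contrast is named

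*SAP*

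**What the plan says.** SAP 7.3.2.9 plans two analyses of the duration of combined CR and CRh.

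- **Responders only.** Duration is "analyzed using the Kaplan-Meier method for subjects who achieved a CR or CRh during the study". For the contrast between arms in this subset, the SAP names a log-rank test without stratification.
- **All subjects.** To bring the share of responders into the result, a separate analysis is "conducted with a 0-day event duration assigned to subjects who did not achieve a CR or CRh". Its named output is: "The median and quartiles of duration of complete response, as well as their respective 95% CIs will be provided". No test, hazard ratio, mean or difference is named for it.

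Protocol 11.6.2.8 has the same 0-day rule. It plans Kaplan-Meier estimation among responders and names no test; the responders-only log-rank appears first in the SAP.

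Three other places matter. SAP 7.3.2.6 compares the CR, CRh and CR+CRh rates in all randomized subjects by a stratified Cochran-Mantel-Haenszel (CMH) test, with a weighted difference and 95% CI. SAP 7.3.3 makes duration supportive and keeps it outside the hierarchy. It also foresees treatment differences with 95% CIs where they apply, but names neither the statistic nor the population.

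**The concern.** The all-subjects analysis is the part of the duration plan that preserves randomization. Its purpose is to combine how many patients respond with how long they stay in response. If most patients do not respond, low-order quantiles show neither.

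The responders-only log-rank will return a p-value, but it compares subsets selected on an outcome of treatment. A drug that brings more marginal patients into response can then look worse on duration, even if no patient's response is shortened. A supportive endpoint would rest on that comparison, while the randomized analysis offered little to set against it.

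**Working it through.** **Inputs**

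- Non-responders count as events at day 0 (SAP 7.3.2.9), so the all-subjects Kaplan-Meier curve has S(0) = r, the CR+CRh rate.
- "CRh will also be assessed as a subset of CRi or CRp who have partial hematologic recovery" (SAP 7.3.2.5). Hence CR ≤ CR+CRh ≤ CRc. Phase 2 reported CR and CRc but not CRh, so r can only be bounded.
- Phase 2 rates: "10-day CRc and CR rates, 30% and 19%, respectively; 5-day CRc and CR rates, 16% and 8%, respectively" (Protocol 1.5.1.2). Overall, CR was 14/103 = 13.6% and CRc 24/103 = 23.3%.
- TC proxy: CR+CRi of 21% in the treatment-choice arm of the phase 3 relapsed/refractory trial cited in Protocol 2.1. CR+CRi is not the same endpoint as CR+CRh.
- About 300 randomized (Protocol 4.1), taken as 150 per arm.

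**Reproducing the plan's figures.** SAP 7.3.2.9 gives no number. The Phase 2 figures that bound r do reproduce with exact binomial intervals: 16/53 = 30.2% [18.3, 44.3] and 24/103 = 23.3% [15.5, 32.7].

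**When each quantile is 0.** A quantile is the smallest t at which S(t) falls to 0.75, 0.50 or 0.25. So:

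- the lower quartile is 0 if r ≤ 75%;
- the median is 0 if r ≤ 50%;
- the upper quartile is 0 if r ≤ 25%; otherwise it is the (1 − 0.25/r) quantile of responders' durations.

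At 150 per arm, the lower quartile and median are 0 with probability above 0.9999 for every r from 8% to 30.2%. Even the upper confidence limit for 10-day CRc, 44.3%, lies below 50%.

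For the upper quartile (exact binomial, 37 or fewer responders of 150):

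| True CR+CRh rate | Source of the rate | P(upper quartile = 0) |
|---|---|---|
| 16% | 5-day CRc | 0.998 |
| 18.9% | 10-day CR (floor) | 0.97 |
| 21% | cited TC rate | 0.88 |
| 23.3% | overall CRc | 0.69 |
| 25% | threshold | 0.51 |
| 27% | within 10-day range | 0.29 |
| 30.2% | 10-day CRc (ceiling) | 0.08 |

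Results for 140 and 202 per arm are close: 0.90 and 0.92 at 21%, 0.10 and 0.05 at 30.2%.

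Where the upper quartile is above 0, it describes the shortest responses: 1 − 0.25/0.302 = 0.17, the 17th percentile of responders' durations.

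**Confidence limits.** Using the log-log interval that SAP 7.3.1 names for OS (an assumption here), 30/150 responders give a CI for S(0) of 0.14 to 0.27. This includes 0.25, so the CI for the upper quartile can extend above 0. At 27/150 it is 0.123 to 0.245, which excludes 0.25.

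**What a mean would show.** The documents give no response durations, so assume a restricted mean among responders of 100 to 300 days, equal in both arms, with rates of 30.2% and 21%.

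- At 100 days: 30.2 vs 21.0, difference 9.2 days.
- At 300 days: 0.302 × 300 = 90.6 vs 0.21 × 300 = 63.0, difference 27.6 days.

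The median and lower quartile are 0 in both arms throughout.

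**Direction of the responders-only bias (assumed values).** Let prognosis u be uniform on 0 to 1. Control patients respond if u < 0.19 and drug patients if u < 0.30. Mean duration is 400·exp(−4u) days in either arm, so the drug changes no patient's duration.

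- Area for control: 100(1 − e^−0.76) = 53.2 days. Among responders: 53.2/0.19 = 280 days.
- Area for drug: 100(1 − e^−1.2) = 69.9 days. Among responders: 69.9/0.30 = 233 days.

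The responders-only mean is 47 days worse on the drug, while the all-subjects mean is 16.7 days better. With no prognostic gradient, the responders-only gap is 0.

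In 2000 simulated trials under these values, with 150 per arm and no censoring, the responders-only log-rank pointed against the drug in 75%. It was significant against it in 11%, where 2.5% is nominal.

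**The case against.** A reader might infer that all three quartiles will be 0 in both arms, so that the analysis must return zero against zero. The documents do not support that. The guadecitabine arm starts on a 10-day regimen, whose Phase 2 range of 18.9% to 30.2% spans the 25% limit. At 30.2% vs 21%, the chance of an upper quartile above 0 on guadecitabine and 0 on TC is about 0.92 × 0.88 = 0.81. That would be a visible difference in the expected direction, and the confidence limits need not be 0 either.

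A reader might also infer that the plan leaves no randomized comparison bearing on response. It does not go that far. The CR+CRh rate is tested in all randomized subjects and stands fifth among the secondary endpoints in the hierarchy, so an adverse responders-only result would be read beside it. SAP 7.3.3 also leaves room for a difference with a CI.

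The endpoint is supportive, no success criterion rests on it, and enrollment stopped for futility on OS. The size of the responders-only bias cannot be derived from the documents.

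All of this stands and limits the consequence. It does not close the gap. The rate test says nothing about duration, and the sentence in SAP 7.3.3 names no statistic; applied to the planned median it gives 0 minus 0. An upper quartile that reflects only the shortest responses is a poor measure of time in response.

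**Conclusion.** The point holds in a limited form. At the response rates the documents support, about 8% to 30%, the all-subjects median and lower quartile will be 0 in both arms. The upper quartile will also be 0 in any arm with CR+CRh of 25% or less: likely for TC (0.88 at 21%), and anywhere from 0.97 to 0.08 for guadecitabine across its Phase 2 range. No between-arm contrast is named for this analysis, and the only duration test named compares groups formed after randomization.

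This rests on about 150 subjects per arm, on Phase 2 rates carrying over, and on CR+CRi as a proxy for the TC rate. The simulation shows the direction of a possible bias; it is not a forecast. The primary endpoint and the testing order are unaffected. The change is worth making because it is cheap and lets the analysis do its stated job.

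**What to change.** In SAP 7.3.2.9, for all randomized subjects:

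- Report restricted mean time in CR/CRh by arm over a prespecified horizon, with the stratified difference and 95% CI. Twelve months from randomization fits, since SAP 7.3 places the analysis at least 12 months after the last randomization. Use the same strata as for OS, including any collapsing under SAP 7.3.5.
- As an acceptable alternative with less change, apply a log-rank test stratified by the randomization factors to the all-subjects data already planned.
- State in SAP 7.3.3 that this is the difference meant for the endpoint.
- Keep the responders-only Kaplan-Meier curves as description, and do not use their log-rank p-value as evidence of treatment benefit.

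The cost is SAP wording, one extra summary from dates already collected, and a horizon to fix in advance.

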7.3.2.10 EQ-5D-5L Descriptive System Total Score and the EQ VAS

The EQ-5D-5L descriptive system scores and the EQ VAS were collected for each subject for a minimum 6 months unless the subject died or withdrew consent prior. The calculation for EQ-5D-5L index value will be performed according to EuroQol group's EQ-5D-5L User Guide (http://www.euroqol.org/about-eq-5d.html). Since there are only a limited number of countries which have rules available for calculating EQ-5D-5L index values, the rules for England (Devlin et al 2016) will be used for all subjects from all countries in this study. These analyses will include only the data collected for each subject during the first 6 months of study participation.

As suggested in the EQ-5D-5L User Guide (http://www.euroqol.org/about-eq-5d.html), the EQ-5D-5L descriptive scores and their dichotomized levels (No problems, Problems) within each EQ-5D dimension (mobility, self-care, usual activity, pain/discomfort, anxiety/depression), will be summarized by time (ie, visit/treatment cycle) descriptively, using counts and proportions. The EQ-5D-5L index value and VAS and their respective changes from baseline will be summarized by time (ie, visit/treatment cycle) using means, standard deviations, medians, and quartiles.

In addition, the changes from baseline (post baseline value – baseline value) of EQ-5D-5L index value, and separately EQ VAS, will be analyzed using a mixed model approach for repeated measures. This model will include the following terms as fixed effects: baseline value, treatment, time, and treatment-by-time interaction. The unstructured covariance matrix will be used to account for the within subject correlation and allow for different variances at different measurement times. The difference of the least squares means between the two treatment groups at each time (ie, visit/treatment cycle) and its corresponding 95% CI will be provided.

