5.0 ANALYSIS SETS

5.1 Efficacy Analysis Set

Efficacy analyses will be based on intent-to-treat (ITT) principle. The Efficacy Analysis Set will include data from all subjects randomly assigned to study treatment. All data will be included and no subjects excluded because of protocol violations. For the analysis of efficacy data, subjects will be included in the treatment group according to their randomly assigned treatment.

For NDAOH, and health-related QOL by EQ-5D-5L, the primary analysis will include only the data collected during the first 6 months of the study because, during this study period, subjects are assessed monthly whether or not they are still on study treatment. Secondary analysis, if performed, may also include data beyond the first 6 months of the study (eg, over the entire study period until disease progression).

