7.3.2.3 Number of Days Alive and Out of the Hospital

The date of each hospital admission and discharge were collected for each subject for at least 6 months (and until disease progression for subjects who had not progressed during the first 6 months or until the subject died or withdrew consent prior).

The duration of each individual hospital stay in days (regardless of the reason for hospitalization) is calculated as:

Duration of individual hospital stay = date of discharge – date of admission

For a subject who was admitted and discharged on the same day, the duration of hospital stay will be 0. The total duration of all hospital stays in the first 6 months is the sum of the durations of all individual hospital stays occurring between date of randomization and Day 180. For ease of calculation, one month is defined as 30 days for analyses conducted in this study.

The NDAOH within the first 6-month period is calculated as:

NDAOH6M = 180 - total duration of all hospital stays - number of death days before Day 180

For subjects who died within the first 6-month period, the number of death days before Day 180 is calculated as:

Number of death days = (date of Day 180 - date of death)

For subjects who died on or after Day 180 the number of death days before Day 180 will be set to 0.

For subjects who were lost to follow-up within 6 months (expected to be a very small number), the NDAOH will be calculated conservatively assuming that the subject would have died the day after the last contact day.

The NDAOH6M will be summarized by treatment group and comparisons between the 2 treatment groups will be performed using an analysis of variance (ANOVA) model at an overall alpha level

of 0.05, as further described in Section 7.3.3. The variables used for stratification at randomization will be included in the analysis of variance model as fixed factors.

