7.8 Handling of Missing Data and Other Data Anomalies

No missing data imputations are planned for the study, except as specified. Subjects lost to follow-up will be included in statistical analyses to the point of their last evaluation.

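### The EQ-5D index and EQ VAS repeated-measures models leave out the randomization strata and have no rule for death, so their precision is not protected and what they estimate is not stated

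*SAP*

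**What the plan says.** SAP 7.3.2.10 states that changes from baseline in the EQ-5D-5L index, and separately in the EQ VAS, "will be analyzed using a mixed model approach for repeated measures". The terms are listed in full: "This model will include the following terms as fixed effects: baseline value, treatment, time, and treatment-by-time interaction". On covariance: "The unstructured covariance matrix will be used to account for the within subject correlation". On the window: "These analyses will include only the data collected for each subject during the first 6 months of study participation". The output is the difference in least-squares means at each visit with a 95% CI. Protocol 11.6.2.9 names the type of model and no covariates.

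On data collection, SAP 7.3.2.10 says the scores "were collected for each subject for a minimum 6 months unless the subject died or withdrew consent prior", and SAP 5.1 adds that in this period "subjects are assessed monthly whether or not they are still on study treatment". SAP 7.8 says: "No missing data imputations are planned for the study, except as specified". Nothing is specified for EQ-5D after death.

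NDAOH (SAP 7.3.2.3), over a six-month window, does cover both matters. Days after death are subtracted, and "The variables used for stratification at randomization will be included in the analysis of variance model as fixed factors". SAP 7.3.3 puts quality of life outside the hierarchy, as support for a claim of benefit.

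**The concern.** Two things are missing from the model.

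**Strata.** SAP 3.1 explains that TC intensity, ECOG status, cytogenetics and region were chosen because they predict outcome, and that stratifying on them was meant to limit bias and raise power. OS, EFS, one-year survival, NDAOH, transfusion independence, CR+CRh, CRc and HCT rate are all stratified by these factors or adjusted for them. The EQ-5D term list is explicit and omits them. At stake is a little precision. The missing-data assumption is also harder to defend when ECOG status and intended intensity, which plausibly relate to both health status and survival, are not in the model.

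**Death.** A likelihood-based repeated-measures model with no rule for death treats a score absent because the subject died like a form that was not returned. Its later means then describe, in part, subjects who no longer exist. The reader of the report would see month-by-month differences with confidence intervals and no statement of the population they refer to. SAP 7.3.3 plans these differences and intervals outside the gatekeeping sequence.

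**Working it through.** **1. The planning figures reproduce.** The documents give no sample size, SD or effect size for EQ-5D, so the only figures to check are those for OS in SAP 4.0: medians 4.5 and 6.5 months, HR 0.692, two-sided alpha 0.05, 1:1 allocation.
- Power at 315 deaths: Φ(√315/2 × |ln 0.692| − 1.960) = Φ(3.267 − 1.960) = 0.904; stated as at least 90%.
- Power at 277 deaths: Φ(3.064 − 1.960) = 0.865; stated as 86%.
- Accrual: 3+6+9+12+15+18+21+24+27+29 = 164, plus 8 × 30 = 240, total 404.

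**2. Deaths inside the EQ-5D window.** With exponential survival, the share dead at month t is 1 − 0.5^(t/median).

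| Month | TC (4.5) | Guadecitabine (6.5) |
|---|---|---|
| 3 | 37.0% | 27.4% |
| 6 | 60.3% | 47.3% |

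The protocol synopsis gives about 300 randomized. With 150 per arm, about 150 × 0.397 = 60 TC and 150 × 0.527 = 79 guadecitabine subjects are alive at month 6, or 139 of 300. The planned dropout of 0.012 per month gives 1 − 0.988^6 = 7.0% over six months, so on the plan's own figures death is by far the larger cause of missing scores.

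**3. Effect of adding the strata.** As main effects the factors cost 2 + 1 + 1 + 1 = 5 degrees of freedom. If they explain a share R² of the residual variance left after baseline, the standard error is multiplied by √(1 − R²). R² is assumed.

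| R² | SE ratio, formula | SE ratio, simulated |
|---|---|---|
| 0 | 1.000 | 1.000 |
| 0.02 | 0.990 | not run |
| 0.05 | 0.975 | 0.979 |
| 0.10 | 0.949 | 0.956 |

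The simulation fitted the model by maximum likelihood with unstructured covariance: 300 subjects, six monthly visits, data ending at death, 300 replicates.

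**4. What the model estimates when subjects die.** The same simulation had no true treatment effect. The log hazard of death fell by 0.6 per SD of an unobserved health level (an assumption). Month-6 differences, guadecitabine minus TC, in residual SD units:

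| R² | Survivors only | SAP model | All, as if alive |
|---|---|---|---|
| 0 | −0.079 | −0.047 | 0.004 |
| 0.05 | −0.052 | −0.019 | 0.012 |
| 0.10 | −0.060 | −0.030 | 0.007 |

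With the link to health removed (R² = 0.05), the three values were 0.016, 0.009 and 0.009, all close to zero. When death depends on unobserved health, the model lands between the two contrasts and equals neither. The distances here are 0.03 to 0.05 SD, against a standard error of about 0.15. Adding the strata did not remove the gap: the model estimates became −0.047, −0.020 and −0.038.

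**The case against.** Much can be said for leaving the plan alone.

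- **SAP 7.3 already names the randomization factors for use in the analyses.** That sentence says which factors apply where an analysis is stratified. It does not add terms to an explicit list that leaves them out.
- **Supportive endpoints are consistently unadjusted.** Duration of CR+CRh, the other endpoint outside the hierarchy, is compared with a non-stratified log-rank test. This is true, and it makes adjustment an improvement rather than the repair of an error.
- **The precision gain may be nil.** Baseline EQ-5D is already in the model and may carry most of what ECOG status would add. This stands.
- **Death is counted elsewhere,** in OS and NDAOH, and the by-visit summaries use observed scores. This also stands; the point concerns the mixed model only.
- **The SAP never says missing at random.** That is an inference from the model type and the absence of any death rule.

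Three stronger readings are tempting. A reader might infer that projecting past death flatters guadecitabine. On the planning medians TC has more early deaths, so a bias towards the arm with more deaths would favour TC. The gap between arms also assumes HR 0.692, which the futility finding makes doubtful. A reader might want to call the result conditional on being alive, but step 4 shows it is not a survivor contrast. A reader might convert the precision gain into a number of extra subjects. The documents give no residual variance, and only about 139 of 300 would be alive at month 6, so no such number can be supported.

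**Conclusion.** Both gaps are real, and neither document fills them elsewhere. Severity is minor: no alpha-controlled conclusion depends on EQ-5D.

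Omitting the strata does not by itself bias the comparison. Including them is worth about 0 to 5% of the standard error for an assumed R² of 0 to 0.10.

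The lack of a death rule matters more. About 60% (TC) and 47% (guadecitabine) would be dead by month 6, assuming exponential survival at the planning medians. If survival is similar in the two arms, the imbalance shrinks, but about half the subjects still die in the window: 47% if both medians are 6.5 months, 60% if both are 4.5. The later least-squares means therefore depend on an implicit as-if-alive, missing-at-random assumption and do not compare survivors. The direction and size of any bias are not established; the simulated figures illustrate one assumed link between health and death.

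**What to change.** 1. In SAP 7.3.2.10, add TC intensity, ECOG status, cytogenetics and region as fixed effects in both the index and the VAS model, collapsed as for OS under SAP 7.3.5. Cost: one sentence and up to five parameters per model.
2. State that the mixed-model estimates rest on an as-if-alive assumption and do not estimate a difference among survivors. Report the number alive and the number assessed at each visit, by arm. Cost: wording and two rows of counts from data already collected.
3. Optionally, add one supportive analysis of all randomized subjects that gives death a pre-stated value for the index and another for the VAS, with a rule for visits missed while alive. Zero for the index would be an assumption, since the documents give no anchor, and they suggest no value for the VAS. Cost: one table and a second estimand to explain. With about half the subjects dying, the result will be driven largely by survival and will partly repeat OS and NDAOH.
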